Number of Participants:	N=24 (n=12 in Australia and n=12 in Singapore) Accounts for 20% attrition.
Inclusion/Exclusion Criteria:	
INCLUSION CRITERIA:
 
 1. Healthy men, 21-50-year old 2. BMI 18-27.5 kg/m^2 3. Consuming <2 meals of fatty fish/week and no fish oil supplements 4. Ethnicity 
 ○ If Australian site: Australian European 
OR
 
 ○ If Singapore site: Chinese Singaporean 
EXCLUSION CRITERIA:
 
 1. Self-reported history of chronic disease - cancer, type 2 diabetes, cardiovascular disease, liver disease or any condition that may, in the opinion of the principle investigator, influence the study outcomes. 2. Self-reported history of gastrointestinal disease, pancreatic insufficiency, conditions resulting in fat malabsorption - chronic pancreatitis, cystic fibrosis, coeliac disease, Crohns disease, gastric bypass surgery, small bowel resection, abnormal thyroid function 3. Bleeding disorders, currently taking anticoagulants or has received anticoagulants within 28 days of Day 1 of the trial, with the exception of low dose aspirin up to 150 mg daily* 4. Any medical procedures deemed by the principal investigator to affect study outcomes

	
 5. Known food allergies, hypersensitivity, dietary avoidance or intolerance to the study foods 6. Taking medications/supplements known to influence lipid metabolism and gastric emptying 7. On any weight-loss program 8. History of smoking during the 6 months prior to the study 9. Persons considered by the investigator to be unwilling, unlikely or unable to comprehend or comply with the study protocol. 10. Self-reported history of drug abuse or alcoholism 11. Participation in another research study within 30 days preceding the start of this study
Treatment:	
Standardised breakfast plus:
 
Test food 1: Semi-solid food – Soup (commercially available packet-soup) containing cauliflower encapsulated HiDHA® algal oil providing 400 mg DHA
 
Test food 2: Solid food – Extruded snack (savory snack) containing cauliflower encapsulated HiDHA® algal oil providing 400 mg DHA
 
Control: 2x Algal oil gel capsules containing HiDHA® algal oil providing 400 mg DHA

Study Duration:	~1 month (3 test products at least 1-week apart)
Study Population:	Healthy men
Primary Outcome:	Plasma DHA and total omega-3 LCPUFA iAUC _{0-24h}

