heating at 90 °C; addition of 2 mL methanol; acidification with 200 µL of acetyl chloride and heating at 90°C for 1 hr while vortexing approximately every 10min after which the samples will be returned to room temperature. Methyl esters will be extracted into 1.5 mL hexane and 1.0 µl aliquot injected onto a gas chromatographic column (DB – FastFAME, 20m x 0.18 mm from Agilent Technologies), using a PerkinElmer Clarus 690 gas chromatograph / Clarus SQ 8 T Mass Spectrometer with a split 50:1 injector. Fatty acids will be identified by comparison with authentic Sepelco 37 component FAME mix (Sigma-Aldrich, Australia) and verified using the NIST MS search database software. Peaks will be measured using TurboMass software and fatty acids will be calculated against the internal standard.

8. Statistical analysis

A sample size of n=10 per site provides >80% power to detect a difference of 10% in AUC (22). N=12 per site will be recruited to account for a 20% attrition rate.

A statistical analysis plan will be developed before statistical analysis commences. In brief, data will be presented as means and SD/SEM. Plasma DHA and total omega-3 LCPUFA concentrations will be plotted into graphs. $iAUC_{0-24h}$ (primary outcome), will be calculated using the trapezoidal rule and corrected to baseline levels. Time to maximal value (Tmax) and the maximal value (Cmax) will be determined. Primary analysis will be pairwise comparisons between test foods vs. control using linear mixed models with fixed effects for treatment, time, ethnicity and assessing the interaction of treatment*time and treatment*time*ethnicity. Participant identifier will be fitted as a random effect, i.e. one intercept per participant. Potential covariates will be identified *a priori* and included in the model (e.g. BMI). Intention-to-treat analysis will be performed primarily and per protocol analysis as secondary analysis.

Statistical analysis will be performed using appropriate statistical packages e.g. SPSS software (IBM Corporation, New York, USA). Statistical significance will be determined at a *P*-value of <0.05. Statistical analysis will be performed blinded and treatments revealed after completion of the statistical analysis.

9. Assessment of Adverse Events

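### Twelve recruits per site do not cover 20% attrition from the 10 per site behind the power statement; they cover two withdrawals, or 16.7%

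*Combined protocol and SAP*

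**What the plan says.** Section 8 (Statistical analysis) makes two linked statements. The first gives the basis for the sample size: "A sample size of n=10 per site provides >80% power to detect a difference of 10% in AUC". It is supported by a literature citation, with no SD, CV or exact power. The second turns that number into a recruitment target: "N=12 per site will be recruited to account for a 20% attrition rate".

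The synopsis, under Number of Participants, gives the same target for the whole trial: "N=24 (n=12 in Australia and n=12 in Singapore) Accounts for 20% attrition".

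Neither place shows the formula behind the allowance. Section 8 makes the intention-to-treat analysis primary and plans linear mixed models with a random intercept per participant and ethnicity as a fixed effect.

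**The concern.** An attrition allowance is meant to leave, after the expected losses, the number on which power was stated. Here that number is 10 per site, the only one for which the plan gives a power figure. Applying the plan's own 20% to its own 12 does not return 10. The likely cause is that the rate was applied to the completers (10 plus 20% of 10) and not to the recruits who are exposed to it.

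What is at stake is the accuracy of the sample-size statement, which will otherwise pass into the statistical analysis plan and the publication. A reader would take it that the trial still has its stated power after one in five participants leaves. On the plan's figures that is not quite so.

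**Working it through.** **Inputs.** From section 8: 10 per site for power above 80%, 20% attrition, 12 recruited per site. From the synopsis: 24 in total. Significance is set at P<0.05 with no sidedness given; two-sided is assumed below, for the power illustration only.

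**Reproducing the plan's figure.** n × (1 + d) = 10 × 1.2 = 12 per site, and 20 × 1.2 = 24 in total. Both match the plan exactly.

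**Standard inflation.** n / (1 − d) = 10 / 0.8 = 12.5, rounded up to 13 per site (26 in total). Applied to the pooled 20, it gives 20 / 0.8 = 25.

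**What 12 delivers at 20% attrition.**
- Per site: 12 × 0.8 = 9.6, which is 0.4 below 10.
- Overall: 24 × 0.8 = 19.2, which is 0.8 below 20.
- Attrition that 12 does cover: (12 − 10) / 12 = 16.7%.

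**Chance of reaching 10 completers in a site**, assuming independent 20% dropout (binomial):

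| Recruited per site | One site reaches 10 | Both sites reach 10 | At least one site falls short |
|---|---|---|---|
| 12 | 0.558 | 0.558² = 0.312 | 0.688 |
| 13 | 0.747 | 0.747² = 0.558 | 0.442 |

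**Effect on power.** The plan's figure cannot be reproduced without a variance. As an illustration, assume a within-site paired t-test, two-sided at 0.05. Take three values of power at n=10, solve for the SD of the paired difference (as a percentage of the control mean, for a 10% effect), and recompute with the noncentral t distribution:

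| Power at n=10 (assumed) | Implied SD of difference | Power at 9.6 | Power at n=9 |
|---|---|---|---|
| 80% | 10.0% | 78% | 74% |
| 85% | 9.4% | 83% | 80% |
| 90% | 8.7% | 88% | 86% |

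The first row is the least favourable case, because the plan says only that power exceeds 80%.

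**The case against.** The case on the other side has four parts.

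1. **Ten is not a stated minimum.** The plan says 10 per site gives more than 80% power. It sets no target and no required number of completers, so there may be slack. That is fair, and it is why no single power loss can be claimed. It does not rescue the sentence about attrition, which is a statement about 12, 20% and 10.

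2. **The illustration is not the planned analysis.** The mixed model includes both sites. If the SD of the paired difference equals the 10% effect, a paired t-test pooled over sites has about 98.9% power with 20 participants and 97.9% with 18, so one site at 9 would hardly matter for the overall comparison of test food with control. This stands under that assumption. The plan does not say which comparison its power figure refers to, and it gives none for the interaction with ethnicity.

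3. **Dropouts still contribute data.** Participants receive their first test product on the day of enrolment, and someone who leaves after two periods can still inform a contrast. This stands in part. A participant who misses one of the two products being compared adds little within-person information on that comparison.

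4. **The gap is one participant per site.** True, and the point is rated accordingly.

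A reader might infer more: that the trial is underpowered, that power falls to about 75%, or that the error makes it likely that a site falls short. The documents do not support these readings. The figure near 75% needs an SD that the documents do not give and the lowest power that they allow. The chance that at least one site falls below 10 is 69% with 12 per site, but still 44% with 13, so much of it is ordinary variation that correct inflation would not remove.

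**Conclusion.** The attrition statement is wrong as written, in section 8 and in the synopsis. Twelve per site covers 16.7% attrition; at 20% the expected number of completers is 9.6 per site. This follows from the plan's own numbers and needs no outside assumption.

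The size is small: 0.4 of a participant per site in expectation, and one per site after rounding up. Any cost in power is undetermined. The range of 74% to 86% at 9 completers depends on an assumed power of 80% to 90% at 10 and on a completers-only paired t-test within one site. The planned analysis of both sites, with partial data retained, would lose less. The finding is an inaccurate sample-size statement, and it does not show that the design is inadequate.

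**What to change.** In section 8 and in the synopsis, replace the 20% claim with a statement that 12 per site allows for 2 withdrawals per site (16.7%). Section 8 should also give the variance assumption taken from the cited source, name the comparison that the power refers to, and restate power at 9 completers per site next to the figure at 10. Only the sponsor can supply that number, because the variance is not in the documents. The corrected text should carry into the statistical analysis plan.

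The cost is wording in two places and one recalculation. The stated allowance becomes slightly less favourable. Recruitment, design and analysis are unchanged. If the sponsor prefers to keep a 20% allowance, the matching figure is 13 per site, but correcting the statement does not require it.

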I, the undersigned, have reviewed this protocol, including the appendices and I will conduct the study as described in compliance with this protocol, GCP and relevant International Council on Harmonisation (ICH) guidelines.

Once the protocol has been approved by the Human Research Ethics Committee (HREC), I will not modify this protocol without obtaining prior agreement and approval from CSIRO/A*STAR Principal Investigator (PI) and the HREC. I will submit the protocol modification and/or any Informed Consent Form (ICF) modifications to the CSIRO/A*STAR PI and HREC and approval will be obtained before any modifications are implemented.

I understand that all the information obtained during the conduct of the study with regard to the participants' state of health will be regarded as confidential. No participants' names will be disclosed. All Participants will be identified by assigned numbers on all case report forms (CRF), laboratory samples or source documents. Clinical information may be reviewed by regulatory agencies. Agreement must be obtained from the participant before disclosure of participant information to a third party.

INVESTIGATOR SIGNATURE:

PRINTED NAME: [name]

COMPANY/POSITION: CSIRO

SIGNATURE: 

INVESTIGATOR SIGNATURE:

PRINTED NAME: [name]

COMPANY/POSITION: A*STAR

SIGNATURE: 

Study Synopsis

Protocol Title:	Bioavailability of omega-3 long-chain polyunsaturated fatty acids (LCPUFA) from foods enriched with vegetable-encapsulated omega-3 oils
Aim:	To compare the bioavailability of omega-3 LCPUFA from two test food products containing vegetable-encapsulated omega-3 algal oil against a control test product (algal oil gel capsules) across two ethnicities (Australian European vs. Chinese Singaporean).
Study Design:	Multi-centre, randomised, controlled, acute, 3-way cross-over study design. Participants will consume in random order, at least 1-week apart, three test products after an overnight fast. Blood samples will be collected at 0, 2, 4, 6, 8 and 24 hours after consuming the products. Plasma fatty acid concentrations ($\mu\text{g/mL}$) will be analysed by gas chromatography and bioavailability of omega-3 LCPUFA determined by calculating the incremental area under the curve ($i\text{AUC}_{0-24\text{h}}$), time to maximal value (T_{max}) and maximal value (C_{max}).
Study sites:	CSIRO Nutrition and Health Research Clinic, Adelaide A*STAR Clinical Nutrition Research Centre, Singapore

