Screening occasion: Participants will be pre-screened using a screening questionnaire and those determined to be potentially eligible will be invited to attend an in-clinic screening visit. After they have given signed informed consent (see details below) their eligibility will be confirmed by reviewing their medical history, demographic information and fatty fish intake obtained from the screening questionnaire, measuring height and weight and calculating BMI, and measuring vital signs (blood pressure and temperature). Eligible participants will be enrolled into the study and remain at the clinic for further 8.5 hours and complete their first intervention

Intervention occasions (Figure 2): Participants will arrive at the research clinic after an overnight fast (>10h)). Weight, percentage body fat mass and vital signs (blood pressure and temperature) will be measured, an intravenous cannula will be inserted into the participants arm for a duration of 8 hours during which the participant will remain at the research clinic.

A fasting blood sample (4 mL) will be collected after which participants will consume a standardised breakfast with their test product (see section 5 for more detail) within 15 minutes. Subsequent blood samples will be collected after 2, 4, 6 and 8 hours. The cannula will be removed, and participants will leave the research clinic. Participants will return to the research clinic the next morning after an overnight fast for collection of the 24-hour sample. The period of 24 hours was chosen as it represents an intake interval of daily intake of omega-3 supplements (19). Throughout the 9-hour day at the clinic participants will have access to low-fat snacks and a lunch meal devoid of omega-3 LCPUFA that they can consume *ad libitum* (see section 5 for more detail). Participants will leave the clinic with a take-home low-fat dinner meal.

Apart from the study specific test products, participants will be requested to maintain their habitual lifestyle patterns throughout the duration of the study and to avoid fatty fish and omega-3 LCPUFA containing supplements. Participants will be provided with a checklist to record any non-compliance or accidental consumption of these foods and return the checklist at their subsequent visit.

Staff responsible for sample and statistical analysis will be blinded to which treatment was consumed when, but participants and staff administering treatments will not be blinded.

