The test products will be manufactured in facilities certified for production of food for human consumption in accordance with an approved HACCP (Hazard Analysis Critical Control Point) plan. Only food grade ingredients will be used in the production process. All the equipment that will be used in the production process will be sanitised, swabbed for microbial contamination and recleaned until it becomes suitable for food contact. All the processing steps, from the purchase of the ingredients to the processing and handling conditions at each processing stage will be recorded in a process log sheet. The microbial and physicochemical quality of the final products will be tested in accordance with the approved HACCP plan. The products will be released as fit for human consumption after the Food Risk Assessment Team (FRAT) team examined the process log sheet and the results of the microbial and physicochemical analyses.

7. Assessments

Medical history and demographic information:

Medical and surgical history, medication and supplement use and demographic information will be obtained by questionnaire and interview of participants. This information will be used to screen participants.

Assessment of fatty fish intake:

In order to assess participant's eligibility to inclusion criteria 3 - "Consuming <2 meals of fatty fish/week over the past 3 months", potential participants will be asked to record the frequency and type of fish they habitually consume. E.g. "How often do you consume fish?" Frequency options will include <1x/month, 1-3x/month, 1x/week, 2x/week, 3-4x/week, 1x/day, >1x/day. "What type of fish do you usually consume". The categories of fish according to fatty fish / medium- or low-fat fish sources are summarised in the Appendix and will be used to determine participant's eligibility accordingly.

Anthropometric measurements:

Height and weight will be measured at the screening visit and BMI calculated using the formula: weight (kg)/height (m)². Weight will also be collected at each clinic visit. Height will be measured using a stadiometer and body weight will be measured using calibrated electronic digital scales.

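### The primary iAUC leans on one fasting sample per visit, yet that fasting value is not pre-specified as a covariate, and BMI, the only example named, cannot sharpen the food-versus-control contrasts

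*Combined protocol and SAP*

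**What the plan says.** The Study Synopsis gives the schedule: "Blood samples will be collected at 0, 2, 4, 6, 8 and 24 hours after consuming the products". Section 4 confirms a single pre-dose sample on each test day: "A fasting blood sample (4 mL) will be collected after which participants will consume a standardised breakfast", and then "Subsequent blood samples will be collected after 2, 4, 6 and 8 hours", with the 24-hour sample taken the next morning.

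Section 8 says the primary iAUC "will be calculated using the trapezoidal rule and corrected to baseline levels". It does not say whether area below baseline is subtracted (net) or ignored (positive-only). The primary analysis compares each test food with control "using linear mixed models with fixed effects for treatment, time, ethnicity and assessing the interaction of treatment*time" and the three-way term with ethnicity, plus one random intercept per participant. No fasting DHA or fasting omega-3 term is listed. Potential covariates are to be chosen beforehand "and included in the model (e.g. BMI"; BMI is the only example. Section 7 bases BMI on screening measurements: "Height and weight will be measured at the screening visit and BMI calculated".

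Section 8 describes itself as brief and says a fuller SAP will be written before analysis starts, so a baseline covariate is not ruled out. It is simply not named.

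**The concern.** Subtracting the fasting value does not remove the error in it. That error is carried into the outcome and multiplied by almost the full 24 hours. Because the error is also visible in the fasting value itself, a regression on that value can take some of it back out. The plan collects the measurement at every visit but does not commit to using it this way.

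BMI is a participant-level quantity over a study of about one month. In a cross-over each participant is his own control, so BMI drops out of the food-versus-control contrasts. It may still help the between-participant ethnicity comparison.

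The trial expects about 20 completers, so the primary intervals may be wider than the samples already taken would allow. If the fasting covariate is added only after data have been seen, any gain is open to challenge.

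It is also unclear what the model is fitted to. It contains a time effect and treatment*time, but iAUC has one value per visit and no time dimension.

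**Working it through.** **The plan's own figure.** Section 8 states more than 80% power for a 10% difference in AUC with 10 per site. No SD, CV or within-participant correlation is given, so this cannot be reproduced. A two-sided 5% paired t-test reaches 80% power only if the SD of the within-participant difference is at most 10.0% (n = 10) or 15.1% (n = 20, sites pooled). The calculation below uses 2 × 10 = 20 completers, and 10 for one site alone.

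**Step 1: weights.** Trapezoids at 0, 2, 4, 6, 8 and 24 h give AUC weights 1, 2, 2, 2, 9, 8 (sum 24). Subtracting 24 × C0 gives

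net iAUC = −23·C0 + 2·C2 + 2·C4 + 2·C6 + 9·C8 + 8·C24.

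The weights sum to 0, so a shift that lasts the whole visit, including a stable difference between sites, cancels.

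**Step 2: share of error.** Squared weights: 529 + 4 + 4 + 4 + 81 + 64 = 686. With equal independent error per sample, C0 contributes 529/686 = 77% and the other five samples together 157/686 = 23%.

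**Step 3: what adjustment can recover.** Two assumed ratios are needed:

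- k = variance of a visit-long shift in concentration / error variance of one sample
- V = visit-to-visit variance in absorption / sampling-error variance of iAUC

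Large-sample ratio of standard errors, adjusted to unadjusted:

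√[(157 + 529·k/(k+1) + 686·V) / (686·(1+V))]

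For k = 1, V = 1: √[(157 + 264.5 + 686)/1372] = 0.898.

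**Step 4: at the trial's size.** Three-period cross-over simulation with participant, treatment and period effects, 4000 runs per cell. The covariate is the visit's fasting value as a deviation from the participant's mean. The t intervals use 2N−4 degrees of freedom unadjusted and 2N−5 adjusted. Mean interval width at N = 20, adjusted/unadjusted:

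| | k=0 | k=1 | k=4 | k=16 |
|---|---|---|---|---|
| V=0 | 0.484 | 0.799 | 0.935 | 0.992 |
| V=0.25 | 0.627 | 0.844 | 0.951 | 0.998 |
| V=1 | 0.794 | 0.912 | 0.974 | 1.004 |
| V=4 | 0.934 | 0.976 | 0.998 | 1.010 |

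At N = 10 and V = 1 the ratios are 0.815, 0.929, 1.000 and 1.027 for k = 0, 1, 4, 16. At V = 4, k = 16 the ratio is 1.032. Independent reruns of selected cells agreed to within simulation error, and coverage of the adjusted 95% intervals stayed close to nominal (94.5% to 96.0%).

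**Step 5: in completers.** 20/ratio² at V = 1: 20/0.794² = 31.7, 20/0.912² = 24.0 and 20/0.974² = 21.1 for k = 0, 1, 4.

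**Step 6: BMI.** In a separate REML simulation (24 participants, random intercept, 300 trials per scenario), adding BMI left the standard error at 0.997 to 0.999 of its unadjusted value with complete data, with identical point estimates. With 20% dropout it was 0.996 to 1.000.

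**The case against.** The strongest reply is that section 8 is a summary. It promises covariates chosen in advance, a SAP before analysis, and analysis blinded to treatment. Choosing the covariate after seeing results would depart from the plan, and a baseline-corrected cross-over analysis without the covariate is valid. All of that stands. It is why this is a point about precision and pre-specification and not about invalid inference. It also means the change can still be made in the promised SAP.

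Second, BMI is only an example and has an evident use for the ethnicity objective. That stands too. The criticism is only that BMI does nothing for the primary food-versus-control contrasts.

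Third, the size of the gain is not established. Correct: k and V are assumptions, the results run from about half the width to 3% wider, and for one site alone at V = 1 there is no gain at k = 4 and a loss at k = 16. Against this, the downside is small throughout the range tested.

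Fourth, the gain might depend on the period terms, on net area, or on how the covariate is coded. The first two do not hold up: a rerun at N = 20, k = 1, V = 1 gave 0.914 without period terms, and 0.911 to 0.918 with positive-only area, where the fixed weights no longer apply. Coding does matter. In the REML simulation, with fasting-value stability k/(k+1) = 0, 0.5 and 0.9, a single fasting term gave standard-error ratios of 0.58, 0.90 and 0.98. Splitting it into within-participant deviation and participant mean gave 0.49, 0.80 and 0.97. So the form needs to be written down.

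Fifth, if the model is fitted to concentrations with time 0 as a response, baseline may be handled there. But that would not be an analysis of the stated primary outcome, and section 8 does not say which is meant.

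**Conclusion.** The point holds. The primary outcome gives its largest weight to a single sample per visit, no term for that sample is pre-specified, and the covariate offered as an example cannot help the primary contrasts. The 77% share assumes net area and equal independent errors. The gain from adjustment at 20 completers runs from 52% narrower (k = 0, V = 0) to none (k = 4, V = 4), with 9% at k = 1, V = 1. The worst result tested was 1% wider at 20 completers and 3% wider at 10. Neither k nor V can be derived from the documents. Treatment order is randomised and stable site differences cancel in net iAUC, so this concerns the width of the intervals and not bias. It is a worthwhile, inexpensive improvement to make before the SAP is fixed.

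**What to change.** In section 8 and the SAP:

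1. State that the primary comparison is fitted to iAUC, with one value per participant-visit.
2. State whether the area is net or positive-only.
3. Add to the covariates: the visit's fasting concentration of the same fatty acid measure, as its deviation from the participant's mean over visits, for the treatment contrasts. Do this separately for DHA and for total omega-3 LCPUFA.
4. Add the participant-mean fasting value to the ethnicity comparison only if results are shown with and without it.

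Leave Cmax as defined in section 2.

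The cost is SAP wording and one degree of freedom (36 to 35 at N = 20). No new samples are needed. If the fasting value turns out to be uninformative, intervals could be about 1% wider at 20 completers, or 3% wider within one site.

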- Primary outcome: Incremental area under the plasma DHA and total omega-3 LCPUFA concentration ($\mu\text{g/mL}$) curves ($i\text{AUC}_{0-24\text{h}}$)
- Secondary outcomes: Time to maximal value (T_{max}) and maximal value (C_{max}) on the plasma DHA and total omega-3 LCPUFA concentration ($\mu\text{g/mL}$) curves.

3. Study Population

N=24 (N=12 in Australia; N=12 in Singapore) healthy men. Men are chosen as study population to ensure a homogenous population.

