***Self-reported, no clinical testing will be performed.**

4. Study Design and procedures

A multi-centre, randomised, controlled, acute, 3-way cross-over single-blind study design will be used. The trial will be performed at CSIRO's Nutrition and Health Research Clinic, Adelaide (n=12) and A*STAR's Clinical Nutrition Research Centre in Singapore (n=12).

Participants will attend a screening visit to confirm their eligibility for inclusion into the trial (Figure 1). If eligible, participants will remain at the clinic where they will be enrolled into the study and participate in the first intervention on that day (Screening will be conducted at V1). After enrolment participants will attend the research clinic for test procedures on 3 occasions at least 1-week apart during which they will consume one of three test products at each occasion in random order. Participants will attend the clinic on 6 occasions in total (to include returning for 24hr blood sample) – visits 2, 4 and 6 (Figure 1). A 1-week washout period is sufficient for plasma sample to return to baseline (19). Participants will be randomly assigned by computer sequence generation (<http://www.randomisation.com>) to one of three treatment orders (Figure 1). The random allocation sequence will be generated by a staff member not involved with entering participants into the trial to ensure allocation concealment.

[figure not shown]

Figure 1. Study design

Participants will visit the research clinic on six occasions (Figure 1).

- Occasion 1: Screening + 1st intervention (randomised) involving in-clinic assessments (~9 hours).
- Occasion 2: Participants will return to the clinic for a short visit (30 minutes) where a 24-hour blood sample will be collected (Figure 2).
- Occasion 3: (1 week following Occasion 1) 2nd intervention (randomised) involving in-clinic assessments (~8.5 hours).
- Occasion 4: Participants return to the clinic for a short visit (30 minutes) where a 24-hour blood sample will be collected.
- Occasion 5: (1 week following Occasion 3) 3rd intervention (randomised) involving in-clinic assessments (~8.5 hours).
- Occasion 6: Participants return to the clinic for a short visit (30 minutes) where a 24-hour blood sample will be collected.

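### Cmax is written as the uncorrected plasma peak, so an overall ethnicity effect on it would carry any fasting difference between the groups; define it as an increment over the same-visit 0 h value

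*Combined protocol and SAP*

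**What the plan says.** Section 2 (Outcomes) makes the primary outcome an incremental area. Among the secondary outcomes it lists the "maximal value (C_{max}) on the plasma DHA and total omega-3 LCPUFA concentration" curves, in µg/mL, without the word incremental.

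Section 8 keeps the distinction. The iAUC "will be calculated using the trapezoidal rule and corrected to baseline levels". The next sentence reads "Time to maximal value (Tmax) and the maximal value (Cmax) will be determined", with no correction. The synopsis and section 4 add none.

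The synopsis lists samples at 0, 2, 4, 6, 8 and 24 h. The 0 h sample is taken at each intervention visit: "A fasting blood sample (4 mL) will be collected after which participants will consume a standardised breakfast" with the test product (section 4).

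The mixed model in section 8 has ethnicity as a fixed effect, and "Participant identifier will be fitted as a random effect, i.e. one intercept per participant". No separate model is given for Cmax. Covariates are left open. BMI is the only example, and the 0 h concentration is not mentioned.

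Section 2 expresses the ethnicity question in two ways. The objective asks about the vegetable-encapsulated products relative to the control. The second null hypothesis speaks of bioavailability overall.

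**The concern.** DHA and the other omega-3 LCPUFA are already in fasting plasma, and the Introduction describes plasma DHA as varying with habitual diet. The highest observed concentration is therefore the sum of what the man brought to the visit and what the product added. Only the second part is bioavailability. The sponsor applies this reasoning to iAUC but the text does not carry it over to the peak.

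The exposed comparison is the one between men, not within men. If the two groups differ in fasting DHA, an ethnicity main effect on raw Cmax would show that difference as though it were a difference in absorption, and could disagree with iAUC for that reason alone. The Introduction gives some ground to expect a gap: it says that traits linked to omega-3 status differ between Asian and Caucasian populations. Eligibility (section 4.1) limits fatty fish and excludes recent fish-oil use at both sites, which narrows fasting levels. It sets no limit on the medium- to low-fat fish in the Appendix, so it does not equalise them.

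**Working it through.** The plan gives no figure for Cmax to reproduce. Its only sample-size statement (10 per site, over 80% power for a 10% difference) concerns AUC and gives no SD, so it cannot be transferred to Cmax. All plasma values below are assumptions.

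**1. Which contrasts carry the fasting level.** Let group A have mean fasting level F and group B have F + g. Let the mean rise be R_f on a test food and R_c on the capsules, equal in both groups. Raw Cmax is fasting level plus rise.

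- Food minus capsule, group A: (F + R_f) − (F + R_c) = R_f − R_c.
- Food minus capsule, group B: (F + g + R_f) − (F + g + R_c) = R_f − R_c.
- Ethnicity contrast relative to control: the difference of those two lines = 0. The gap cancels.
- Overall ethnicity effect on one product: (F + g + R_f) − (F + R_f) = g. The gap does not cancel.
- Overall ethnicity effect on incremental Cmax: R_f − R_f = 0.

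**2. Percentage scale.** A 10% difference in the rise changes raw Cmax by 0.1 × rise / (fasting + rise).

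- Fasting 100, rise 10 µg/mL: 1/110 = 0.9%.
- Fasting 40, rise 20 µg/mL: 2/60 = 3.3%.

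The absolute difference (1 or 2 µg/mL) is the same on raw and incremental Cmax; only the denominator grows. On a ratio scale the gap no longer cancels exactly. With F = 40, g = 10, R_c = 15 and R_f = 0.9 × 15 = 13.5, food/capsule is 53.5/55 = 0.973 in group A and 63.5/65 = 0.977 in group B.

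**3. How much of raw Cmax is fasting level.** With r = rise/fasting, the share of the level is 1/(1 + r). The share of between-man variance is CV_b² / (CV_b² + (r × CV_r)²), where CV_b is the fasting CV (20–30%) and CV_r the rise CV (30–60%).

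| r | share of level | share of variance |
|---|---|---|
| 0.1 | 91% | 92–99% |
| 0.25 | 80% | 64–94% |
| 0.5 | 67% | 31–80% |
| 1 | 50% | 10–50% |
| 2 | 33% | 3–20% |

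**4. False-positive rate of the ethnicity main effect at a nominal 5%.** Simulation with 10 men per site, three visits, 2,000 runs per scenario and equal true rise in both groups. Assumptions: fasting mean 40 µg/mL with CV 30%, rise CV 40%, visit-to-visit SD 3 µg/mL on the fasting level and on the rise. The test is a two-sample t-test on each man's three-visit mean.

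| Mean rise (µg/mL) | gap 0 | gap 5 | gap 10 | gap 20 |
|---|---|---|---|---|
| 15, raw Cmax | 5% | 12% | 36% | 88% |
| 40, raw Cmax | 5% | 9% | 18% | 56% |
| 15 or 40, incremental Cmax | 5% | 5% | 5% | 5% |

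In the same runs, the food-versus-capsule and food-by-ethnicity contrasts on raw Cmax stayed at about 5–6%. Monte Carlo error at 5% is √(0.05 × 0.95/2000) = 0.5 percentage points. The simulation subtracts the visit's fasting level without assay error, so it does not show the noise cost of a single 0 h sample.

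**The case against.** The strongest reply has four parts.

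**The crossover protects the main comparisons.** Every man receives all three products and has his own intercept, so a stable fasting level drops out of food versus capsule and out of the ethnicity objective as framed relative to control. This stands on the absolute scale. A reader might infer that raw Cmax weakens the product comparison or confounds every ethnic comparison. Steps 1 and 4 show that it does neither. What remains is the smaller percentage or ratio difference, which matters because the AUC target is in percent and no scale is stated for Cmax.

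**The documents give no plasma values.** This also stands. A reader might infer that Cmax mostly measures habitual DHA status, or that a false ethnic difference would rival the whole product effect. Step 3 shows that the first depends on the ratio of rise to fasting level: the fasting share of between-man variance runs from 99% down to 3% over the range shown. The second is one assumed number divided by another. Nor does the Introduction's remark that baseline status affects response help: it concerns the red-cell Omega-3 Index, not an acute plasma peak.

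**A statistical analysis plan is still to come.** Section 8 describes itself as brief, and an incremental Cmax or a 0 h covariate remains possible. That is fair, but the present text corrects one outcome and not the next, and that plan is due only before analysis starts. Leaving the choice open allows it to be made after concentrations have been seen.

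**Subtraction does not make the ethnic comparison clean.** Each ethnicity is recruited at one site only, so site and ethnicity stay inseparable. This is true, but is no reason to leave a removable component in.

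**Conclusion.** The point holds in a limited form. Followed literally, sections 2 and 8 give an uncorrected peak, and an overall ethnicity effect on it would carry the full fasting gap between the groups, µg/mL for µg/mL, even with equal absorption. This requires that fasting levels differ, that the ethnicity main effect on Cmax is tested or interpreted, and that the 0 h value is not adjusted for. The false-positive rates in step 4 illustrate the mechanism on assumed inputs; they are not estimates for this trial. The bias does not need a small rise: it is still visible when the rise equals the fasting mean.

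Severity is modest. Cmax is secondary and the primary iAUC is already corrected. The change is worth making because it brings Cmax into line with iAUC using a sample already planned.

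**What to change.** In sections 2 and 8, and in the later analysis plan:

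- Define Cmax, for DHA and for total omega-3 LCPUFA, as the largest of the 2, 4, 6, 8 and 24 h values minus the 0 h value of the same visit. Alternatively, analyse the peak with the 0 h concentration as a covariate. The two are not interchangeable for the ethnicity main effect: with an adjustment slope below 1, a part (1 − slope) × gap remains. Choose one before concentrations are seen.
- Report raw Cmax descriptively.
- State which ethnicity contrast is tested on Cmax (overall, or relative to control) and on which scale (absolute or ratio).
- Note that neither definition separates ethnicity from site.

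The cost is a few sentences; no visit, sample or assay is added. The downside is that a single 0 h measurement adds some noise to the difference, as it already does for iAUC.
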